### **6.1.7. Handling of Rescreened Participants**

Rescreening of participants is allowed. If a patient initially screen fails and is subsequently enrolled then that participant will have two subject IDs within the EDC system (one ID for the screen failure and associated data collection, and one ID for the subsequently enrolled participant). The demographics CRF will collect the previous subject ID for rescreened participants. In these cases, the initial screening data collection will be tied to the enrolled subject ID in order to ensure compliance with CDISC standards.

### **6.1.8. Analysis Visit Windows**

By-visit summaries will be based on electronic case report form (eCRF)-defined nominal visits.

In general, analysis of all variables for this study will use the nominal visit or time point as collected on the electronic case report form (eCRF) and/or database. Scheduled visits will be selected over unscheduled visits.

For those subjects who discontinue early from the study and the Early Termination (ET) visit satisfies the following condition:

- 20 days <= the date of ET - the date of the last visit before ET +1 <= 40 days

then the ET visit will be mapped to the next scheduled visit. Otherwise, the ET will not be mapped into any analysis visits.

Adverse events (AEs) and concomitant medications are exceptions to the above rule; all treatment-emergent AEs (TEAEs) and concomitant medications will be presented.

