7.1.1. Drug-Induced Liver Injury Monitoring

Safety laboratory test results will be monitored by a central laboratory in real time with potential drug-induced liver injury (DILI) alerts sent to the Investigator.

For participants with normal liver biochemistries at baseline:

- **Close Monitoring:** An increase of serum ALT or AST to $> 3 \times$ ULN should be followed by repeat testing of ALT, AST, alkaline phosphatase, and total bilirubin within 48 to 72 hours to confirm the abnormalities and to determine if they are increasing or decreasing. Inquiry should also be made about symptoms, strenuous exercise, or previous seizures. Repeat testing 2 or 3 times weekly is recommended. All participants showing possible DILI should be followed until abnormalities return to normal or to the baseline state. If a participant lives remote from the study site, local testing may be performed, and the test results reported to the Investigator (along with the reference ranges for the local laboratory).
- **Study Intervention Discontinuation:** Study intervention will be discontinued when a participant meets one of the conditions outlined below (from 2009 FDA Guidance for Industry-Drug Induced Liver Injury: Premarketing Clinical Evaluation), or if the Investigator believes that it is in best interest of the participant. Safety laboratory

parameters will be monitored by a central laboratory in real time, with potential drug-induced liver injury (DILI) alerts sent to the Investigator.

- ALT or AST $> 8 \times$ ULN
- ALT or AST $> 5 \times$ ULN for more than 2 weeks
- ALT or AST $> 3 \times$ ULN and (total bilirubin $> 2 \times$ ULN or INR > 1.5)
- ALT or AST $> 3 \times$ ULN with the appearance of fatigue, nausea, vomiting, right upper quadrant pain or tenderness, fever, rash, and/or eosinophilia ($> 5\%$)

Close monitoring should be continued. Discontinuation from study intervention does not mean discontinuation from the study, and remaining study procedures should be completed as indicated by the SoA. Participants should be followed until Uox returns to $\geq 80\%$ of baseline.

Patients should be monitored at each study visit and instructed to call the Investigator for new or worsening symptoms of clinical hepatitis. Both symptoms and calls should be captured in dedicated CRFs.

For participants with elevated transaminases at baseline: The following Alternative DILI Monitoring Algorithm should be used.

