| Urine drug screen h                | X                         |           |   |            |            |                 |            |            |            |             |             |             |    |
| Viral serology i                   | X                         |           |   |            |            |                 |            |            |            |             |             |             |    |
| FSH (postmenopausal women)                    | X                         |           |   |            |            |                 |            |            |            |             |             |             |    |
| Study intervention administration             |                           | X         |   |            | X          |                 |            | X          | X          | X           | X           |             |    |
| Spot urine collection j            | X                         |           |   |            | X          |                 |            | X          | X          | X           | X           | X           | X  |
| 24-hr urinary oxalate k            | X                         |           |   |            | X          |                 |            | X          | X          | X           | X           | X           | X  |
| 24-hr urinary creatinine l         | X                         |           |   |            | X          |                 |            | X          | X          | X           | X           | X           | X  |
| Blood draw for vitamin B6 levels m |                           | X         |   |            | X          |                 |            | X          | X          | X           | X           | X           |    |
| Plasma PK sample n                 |                           | X         | X |            | X          | X               |            |            |            |             | X           |             | X  |
| Plasma oxalate sample o            | X                         | X         |   |            | X          |                 |            | X          | X          | X           | X           | X           | X  |
| Record fluid intake p              | X                         | X         |   |            | X          |                 |            | X          | X          | X           | X           | X           |    |

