| EQ-5D-5L hh                            | X                         |           |   |            |            |                 |            |            |            |             |             | X           | X  |
| PedsQL ii                              | X                         |           |   |            |            |                 |            |            |            |             |             | X           | X  |
| Record SAEs jj                         | X                         | X         | X | X          | X          | X               | X          | X          | X          | X           | X           | X           | X  |
| Record AEs kk                          | X                         | X         | X | X          | X          | X               | X          | X          | X          | X           | X           | X           | X  |
| Concomitant medications l              |                           | X         | X | X          | X          | X               | X          | X          | X          | X           | X           | X           | X  |

Abbreviations: ADA = antidrug antibody; AE = adverse event; *AGXT* = the gene that codes for alanine-glyoxylate aminotransferase; anti-dsDNA = anti-double-stranded deoxyribonucleic acid antibody; ECG = electrocardiogram; eGFR = estimated glomerular filtration rate; EOS = end of study; ET = early termination; FSH = follicle stimulating hormone; *GRHPR* = the gene that codes for glyoxylate and hydroxypyruvate reductase; PedsQL = Pediatric Quality of Life Inventory; PH = primary hyperoxaluria; PK = pharmacokinetic; SAE = serious adverse event; SF-36 = Short Form 36 Health Survey; WOCBP = women of childbearing potential

Table footnotes:

- a. Potential participants allowed a second attempt at achieving < 20% variation in 24-hour urinary creatinine excretion, as described in protocol section 8.1.1.1, will be given an extra 7 days within which to complete the second pair of collections. An additional 7 days will also be granted for retest of initially unanalyzable screening laboratory samples.
- b. Day 31 visit to be conducted the day after the Day 30 visit, regardless of when the Day 30 visit occurs within the  $\pm$  2-day window.

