### 6.1.5. Handling of Dropouts or Missing Data

#### 6.1.5.1. Missing Efficacy Endpoint Data

While all possible efforts will be made to ensure that participants stay in the study and all data is collected as scheduled, the occurrence of missing data cannot be completely eliminated.

For the analysis of AUC related efficacy endpoints, based on the MITT or ITT populations, a multiple imputation (MI) approach under the missing-at-random (MAR) assumption will be used to handle missing endpoint data. Subsequently, the AUC related efficacy endpoints will be calculated.

That is, any participant who withdraws or is discontinued from the study or who misses a scheduled visit or assessment through Day 180 will have their missing AUC related efficacy data analyzed as imputed using MI techniques.

Multiple imputation based on a standard MAR imputation approach will be performed in SAS® software using the general approach described below. This strategy is appropriate for data sets that have an arbitrary missing data pattern.

*Step 1:* The Missing at Random (MAR) imputation model will impute missing values using a fully conditional specification (FCS) regression-based multiple imputation model. For participants with missing data at a particular visit, a multiple regression model will be fit that includes the outcome at that visit as the dependent variable and observed data (e.g., outcomes at other visits, treatment, age category [6 to 11, 12 to 17, or ≥18 years], eGFR category [<45 mL/min or ≥45 mL/min], and baseline value of the primary response variable (e.g., Uox or Uox-to-creatinine ratio) as independent variables. This process will be repeated 50 times, resulting in 50 complete analysis data sets. The seed number of 3216549 will be used for the imputation procedure described in Step 1.

SAS pseudo code is provided below:

```
PROC MI DATA=indata OUT=outdata SEED=3216549 NIMPUTE=50;  
  CLASS <treatment> <age category> <eGFR category>;  
  FCS REG (<day 90> <day120> <day 150> <day 180>);  
  VAR <treatment> <age category> <eGFR category> <baseline> <day 90> <day120>  
    <day 150> <day 180>;  
RUN;
```

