### 8.3. Secondary Efficacy Analysis

[figure not shown]
The secondary efficacy endpoints listed below will be summarized by treatment group. A one-sided Wilcoxon Rank Sum test will be used for the comparison between treatment groups for both change and percentage change from baseline for the following outcome variables.

- Change/Percentage change from baseline to Day 180 in the summed surface area of kidney stones
- Change/Percentage change from baseline to Day 180 in the number of kidney stones
- Change/Percentage change from baseline to Day 180 in plasma oxalate (for adults only)

The stone surface area and stone count are defined as follows:

- Stone Surface Area: sum of the measured and calculated surfaces of the stone larger than 5 mm (the longest diameter)
- Stone Count: Stones will be categorized measurable or non-measurable as follows, only measurable stones will be used in the analyses:
  - Measurable : with a minimum size of 5 mm in the longest diameter the surface area of the stones
  - Non Measurable: all other stones, including small stones (longest diameter < 5 mm); if the number is too high, they may just say "too many to count", and / or provide an approximate number

Percentage change will also be calculated for the summed surface area of kidney stones and number of kidney stones using the CT results. These will be listed for each subject for the subgroup of participants from CT sub-study as described in the Protocol Appendix B.

A linear mixed model with observed eGFR as the dependent variable and treatment, study month and the interaction between treatment and month as independent variable, will be used to estimate rate of decline in eGFR response between DCR-PHXC and placebo treatments. A random intercept and slope will be included in the mixed model to fit a different intercept and slope for each subject. In this analysis nominal month will be modeled as a continuous independent factor.

The Least Squares adjusted means will be reported for each treatment group as well as the standard errors and 95% confidence intervals for the LS means. The estimate of treatment effect will be reported as the difference in treatment means, 95% confidence interval for the difference in means, the standard error for the mean difference, and the p-value for the treatment difference.

Example SAS code is provided below for reference:

```
PROC MIXED DATA= METHOD=REML;  
  CLASS <treatment> <participant ID>;  

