#### 8.4. Tertiary/Exploratory Efficacy Analysis

The same statistical model described above for the primary efficacy analysis will be applied to the following tertiary/exploratory efficacy endpoints.

- AUC24-hour Uox from Day 1 to Day 180, based on percent change from baseline (ITT population)
- Percent change in 24-hour Uox from baseline to Day 180 (ITT population)
- AUC24-hour Uox:creatinine from Day 90 to Day 180, based on percent change from baseline (MITT population)
- Change from baseline to Day 180 in the SF-36, EQ-5D-5L in adults, and in the PedsQLTM in children (ITT population)

The number of stone events over a 6-month period will be analyzed using an exact Poisson regression model. The model will include treatment group and baseline stone events rate (continuous). Baseline stone events rate will be the number of stone events observed over the past 12 months prior to dosing. The model will include an offset term for total follow-up time as the 'number of months exposed' equal to the total elapsed time between first dose date and last day of visit in the study, divided by 30.4375. Annualized stone event rate (number of stone events per year per person) will be derived as number of stone events in the exposure period / total number of years exposed.

Example SAS code is given below:

```
PROC GENMOD DATA=;  
  CLASS TREATMENT;  
  MODEL 'Number_stone_evts_6month'=Treatment Kidney_Stone_Event_Baseline  
/OFFSET=Ln_Number_Of_Months_Exposed DIST=POISSON LINK=LOG DSCALE;  
  EXACT Treatment Kidney_Stone_Event_Baseline / ESTIMATE;  
RUN;
```

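### The single 20-to-40-day rule for placing early-termination visits does not fit the closely spaced visits to Day 60, and after a missed Day 150 it leaves an early-termination visit in the Day 180 window unmapped

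*SAP*

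**What the plan says.** SAP section 6.1.8 analyses data by the nominal visit on the eCRF and has one rule for ET visits. The condition is "20 days <= the date of ET - the date of the last visit before ET +1 <= 40 days". If it is met, "then the ET visit will be mapped to the next scheduled visit. Otherwise, the ET will not be mapped into any analysis visits". There is no separate rule for short intervals, for missed visits, or for an ET whose study day lies inside another visit's window. Neither the last visit nor the next scheduled visit is defined further.

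The schedule (SAP Table 1, Protocol section 1.3) is uneven. Visits fall on Days 1, 2, 15, 30, 31, 45 and 60, then every 30 days to Day 180; "Day 31 visit to be conducted the day after the Day 30 visit". The row for "24-hr urinary oxalate" is marked at Screening, Days 30, 60, 90, 120, 150 and 180, and ET. eGFR is marked at the same visits and on Day 1. Neither is planned on Days 2, 15, 31 or 45. Kidney ultrasound is planned only at Screening, Day 180 and ET.

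These parts of the SAP use the resulting visit label:
- The eGFR slope (section 8.3): "In this analysis nominal month will be modeled as a continuous independent factor".
- Multiple imputation (section 6.1.5.1), specified only for AUC-related endpoints. The code imputes "FCS REG (<day 90> <day120> <day 150> <day 180>").
- The exploratory AUC (section 8.4) "from Day 1 to Day 180, based on percent change from baseline (ITT population").
- Plasma oxalate, stone number and stone area (sections 6.1.4 and 8.3), each of which needs a Day 180 value.

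**The concern.** The ET visit is where Uox, eGFR, plasma oxalate (adults), ultrasound, ECG and laboratory values are collected from participants who leave. A gap of 20 to 40 days is a sensible test of whether an ET stands in for the next visit when visits are 30 days apart. When they are 1 to 15 days apart, the same test rejects an ET held on the right day and accepts one held well after the visit it is supposed to replace. When a visit has been missed, it rejects an ET held on the right day for the visit after that.

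Measured values would then be treated as missing or analysed at the wrong time. Plasma oxalate, stone number, stone area and the eGFR slope are steps 3 to 6 of the testing hierarchy in SAP section 6.1.4. With 24 active and 12 placebo participants planned, discarding a measured endpoint value is an avoidable loss.

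**Working it through.** The plan states no figure to reproduce, so the check applies the rule to the schedule.

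**Inputs.** Count = ET date − last visit date + 1, mapped if 20 to 40 (SAP 6.1.8). An ET is therefore accepted 19 to 39 days after the last visit, which gives 21 possible days. Visit days and windows come from SAP Table 1: Days 15, 30 and 45 ±2; Days 60 and 90 ±3; Days 120, 150 and 180 ±5.

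**1. ET held on the next nominal visit day.**

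| Last visit → ET | Count | Mapped |
|---|---|---|
| 1 → 2 | 2 | no |
| 2 → 15 | 14 | no |
| 15 → 30 | 16 | no |
| 30 → 31 | 2 | no |
| 31 → 45 | 15 | no |
| 45 → 60 | 16 | no |
| 60 → 90, 90 → 120, 120 → 150, 150 → 180 | 31 each | yes |

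Within the visit windows, the only early pairs that map are Day 13 → 32 (1 of 25 pairs for 15 → 30) and Days 43 → 62, 43 → 63 and 44 → 63 (3 of 35 pairs for 45 → 60). Attaching the +1 to the last visit date lowers each count by 2, so no early nominal interval maps on that reading either.

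**2. ET coming late after an early visit, with *next* read as next after the last attended visit.**

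| Last visit | Accepted ET days | Label given | Accepted days nearer another visit |
|---|---|---|---|
| 1 | 20–40 | Day 2 | 21 of 21 |
| 2 | 21–41 | Day 15 | 19 of 21 |
| 15 | 34–54 | Day 30 | 21 of 21 |
| 30 | 49–69 | Day 31 | 21 of 21 |
| 31 | 50–70 | Day 45 | 18 of 21 |
| 45 | 64–84 | Day 60 | 9 of 21 |
| 60, 90, 120 or 150 | 19–39 days later | next visit | 0 of 21 |

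After a last visit on Day 45, an ET on Day 84 is labelled Day 60. It is 84 − 60 = 24 days after that visit and 90 − 84 = 6 days before Day 90. At the 30.4375 days per month used in SAP section 8.4, the shift on the eGFR time axis is 24 / 30.4375 = 0.79 month. After a last visit on Day 31, an ET on Day 60 is labelled Day 45, where neither Uox nor eGFR is scheduled.

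**3. The other reading, *next* as next on or after the ET date.** The 30-day visits now fail. After a last visit on Day 90, ETs on Days 121 to 129 go to Day 150, although Day 120 is nearer. After a last visit on Day 150, ETs on Days 181 to 189 have no visit to go to.

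**4. ET inside the Day 180 window (Days 175 to 185).**
- Day 150 attended (Days 145 to 155): 11 × 11 = 121 pairs, of which one fails: 185 − 145 + 1 = 41. With the +1 attached to the last visit date, the one failure is instead Day 155 → 175 (count 19).
- Day 150 missed, last visit Day 120 ±5: the smallest count is 175 − 125 + 1 = 51 and the largest is 185 − 115 + 1 = 71. Every such ET is unmapped.

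In the missed-Day-150 case the participant has a Day 120 assessment, so is in the MITT population. The measured Day 180 Uox is then replaced by imputed values in the primary analysis. Plasma oxalate and stone values have no imputation and drop out.

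**The case against.** Several stronger conclusions are tempting, and the documents do not support them.

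- **That later ETs in general go to the wrong visit.** They do not. With *next* taken as next after the last attended visit, assignment from a last visit on Day 60 onward is always to the nearest visit (0 of 21). Misplacement needs a last visit no later than Day 45, skipped visits, and then an ET.
- **That the most important safety values are lost.** Laboratory extreme-value shifts, ECG extremes and the potentially-clinically-significant counts for laboratory values, vital signs and ECG use every post-baseline assessment, scheduled or not (SAP 9.2, 9.5, 9.6). Adverse events are exempt from the rule, and all data are listed. Only by-visit tables lose an unmapped ET.
- **That the primary analysis is broadly affected.** The imputation model uses baseline and Days 90 to 180, and MITT requires an efficacy assessment after the Day 90 dosing visit. ETs up to Day 60 do not reach it.
- **That participants under liver monitoring lose their ET.** Protocol section 7.1.1 says "Repeat testing 2 or 3 times weekly is recommended", and contacts that frequent would shorten the gap. But the SAP does not say whether unscheduled contacts count as the last visit, and the same protocol section keeps participants who stop treatment in the study. This is an ambiguity, not a demonstrated loss.

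The best remaining objection concerns Day 180. A visit on Days 175 to 185 covers nearly all the Day 180 procedures, and a site could record it as Day 180/EOS, in which case the ET rule never applies. That is fair, so the point holds only for visits recorded as ET. It is also true that two of the six early intervals are next-day visits with no Uox or eGFR, and that the eGFR slope is last in the testing hierarchy.

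**Conclusion.** The concern holds in this form. The rule suits the 30-day visits and fails on the early schedule. At nominal days it maps 0 of 6 on-time ETs through Day 60 and 4 of 4 thereafter. On one reading of *next*, ETs coming late after Day 45 or an earlier visit are labelled with a visit already past, by as much as 24 days when the last visit was Day 45. On the other reading the later visits fail. Neither reading makes the rule work throughout.

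The most consequential case is a missed Day 150 followed by a visit on Days 175 to 185 recorded as ET. Its Day 180 Uox is imputed although measured, and its plasma oxalate and stone values are lost. When Day 150 was attended, the loss is a boundary case (1 of 121 window pairs).

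The effects fall on the eGFR slope, the exploratory Day 1 to Day 180 AUC, by-visit summaries and, in the missed-Day-150 case, the Day 180 endpoints. An unmapped ET eGFR has no nominal month, so the SAP leaves its place in the slope model unclear. The documents give no count of early terminations. With about 36 participants it is likely to be small, so this is worth correcting before lock but does not threaten the trial's main conclusion.

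**What to change.** Replace the gap condition in SAP section 6.1.8 with assignment by study day, in two parts.

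1. **Assessments collected repeatedly** (Uox, eGFR, plasma oxalate, laboratory values, vital signs, ECG): assign each ET assessment to the nearest post-baseline visit at which that assessment is scheduled, using half-interval windows, and only if that visit has no scheduled value. For Uox, for example, Days 75 to 104 go to Day 90 and Day 165 onward goes to Day 180.
2. **Assessments planned only at Screening and Day 180** (ultrasound, echocardiogram, SF-36, EQ-5D-5L, PedsQL): assign the ET to Day 180 only if it falls in the same window around Day 180, for example Day 165 onward. Otherwise list it without mapping. A plain nearest-visit rule must not be used here: it would label an ultrasound on Day 95 as Day 180, which is 180 − 95 = 85 days out and worse than the present error.

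Dropping the gap condition also removes the need to define the last visit. In the section 8.3 slope model, use actual study time rather than nominal month for eGFR.

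The cost is SAP wording and a small change to the visit-assignment program before database lock. No new data or visits are needed.
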